### **10.3. End of treatment / early withdrawal**

The following procedures will be performed at end of treatment / early withdrawal visit:

- Tumor evaluation: PET-CT, CT and/or MRI, if patient stops study treatment for any reason other than disease progression
- Physical examination
- Ophthalmological examination
- Weight
- Vital Signs
- ECOG performance status
- 12-lead ECG: if clinically indicated
- ECHO/MUGA

- Hematology
- Biochemistry
- Serology
- TSH, fT3 y fT4
- Coagulation
- Urinalysis
- Pregnancy test
- Adverse events
- Concomitant medications
- Blood sample: two CPT tubes of 7 ml will be obtained at disease progression (a 2 weeks window is allowed from confirmation of disease progression).
- An image-guided biopsy will be done upon progression. The biopsy is allowed within 4 weeks after the confirmation of disease progression and in any case before starting the next line of treatment.

#### **10.4. Safety follow-up visit**

The following procedures will be performed at Safety follow-up visit at day 30 and 6 months after last study dosage:

- Physical examination
- Ophthalmological examination
- Weight
- Vital Signs
- ECOG performance status
- 12-lead ECG: if clinically indicated
- ECHO/MUGA
- Hematology
- Biochemistry
- TSH, fT3 y fT4
- Coagulation
- Urinalysis
- Pregnancy test
- Adverse events
- Concomitant medications

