## **8.2. Handling of Withdrawals**

The investigator will be requested to collect all patient data until she leave the study treatment. If a subject will be withdrawn by the Investigator or withdraws from the study, the Investigator will complete and report the observations as thoroughly as possible up to the date of withdrawal including the date of last treatment and the reason for withdrawal.

If the subject is withdrawn due to an adverse event, the Investigator will follow the subject until the adverse event has resolved or stabilized.

All patients who are withdrawn from the study should complete protocol specified withdrawal procedures.

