7. Alkaline phosphatase, aspartate aminotransferase (AST), alanine aminotransferase (ALT), $\gamma$ -glutamyltransferase (GGT), total bilirubin; blood urea/blood urea nitrogen (BUN), creatinine: creatinine clearance; glucose, albumin, cholesterol, triglyceride, phosphorus, lactate dehydrogenase (LDH), total protein, uric acid, creatinine phosphokinase (CPK); Sodium, potassium, calcium, magnesium, chloride, bicarbonate (HCO3). Biochemistry will be performed in the 14 days previous to start study treatment.
8. Free T3 and free T4 will only be measured if TSH is abnormal. They should also be measured if there is clinical suspicion of an adverse event related to the endocrine system. In the 14 days previous to start study treatment.
9. Urinalysis: bilirubin, blood, glucose, ketones, PH, protein specific gravity, colour and appearance. Dipstick test every cycle. Additional analyses will be done at investigator criteria in case of abnormal results. Urinalysis will be performed in the 14 days previous to start study treatment.
10. Coagulation tests: prothrombin time, APTT and INR. In the 14 days previous to start study treatment.
11. Serology: hepatitis B surface antigen, hepatitis C antibody, HIV antibody. In the 14 days previous to start study treatment and if clinically indicated thereafter.
12. Serum pregnancy test only pre-menopausal female subjects of childbearing potential. At study entry, every 4 weeks during the study treatment and at the end of study treatment.
13. All formalin-fixed, paraffin-embedded (FFPE) tissue samples block and one hematoxylin and eosin (H&E) stained tumor slide, both obtained in the 15 days before patient inclusion in the study, will be sent to CNIO in order to determine positivity of ERK and/or CDK4/6, preferably obtained after last treatment or the most recent sample as possible (from metastatic site or first diagnosis according to sample availability).
14. Tumor evaluation will be performed every 8 weeks until confirmed PD.
15. 21 days-on/7 days-off.
16. This applies to all non-serious AEs and SAEs that occur at any time during the administration of the study drug and up to 30 days after end of treatment.
17. Concurrent medications administered within the 28 days preceding day 1.
18. Blood sample: two CPT tubes of 7 ml will be obtained at baseline visit before treatment administration, at C2D1 and at disease progression (a 2 weeks window is allowed from confirmation of disease progression).

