## **10.2. Study treatment visits**

Study patients will be evaluated weekly during the first 2 months and every 2 weeks thereafter.

The following procedures will be performed during study treatment:

- Tumor evaluation: PET-CT, CT and/or MRI (every 8 weeks)
- Physical examination: will be performed at screening and thereafter targeting symptoms in subsequent study visits
- Ophthalmological examination: Ask patient for changes in vision at every visit. If change in vision is reported, an ophthalmological examination must be performed preferably within 3 days. Ophthalmologic examination will be performed weekly during first cycle, biweekly during second cycle and every 4 weeks thereafter. Particularly for patients who experience any decrease in visual acuity, or symptomatic or asymptomatic retinal disorders including retinal detachment / RPED / serous retinopathy / retinal vein occlusion (Grade 1 analog to CTCAE v.5) have to undergo ophthalmologic examinations on day 1 of every cycle.
- Weight: in all study visits

- Vital Signs: pulse, blood pressure and temperature; every week during first two cycles, and days 1 and 15 of each cycle thereafter
- ECOG performance status (day 1 of every cycle)
- 12-lead ECG: if clinically indicated
- ECHO/MUGA: before start binimetinib treatment, 4 weeks after the start of treatment and every 12 weeks thereafter.
- Hematology: every week during first two cycles, and days 1 and 15 of each cycle thereafter
- Biochemistry: every week during first two cycles, and days 1 and 15 of each cycle thereafter. Safety laboratory tests can be collected up to 2 days prior to drug administration.
- TSH, fT3 y fT4: day 1 of every cycle. Free T3 and free T4 will only be measured if TSH is abnormal.
- Coagulation: day 1 of every cycle
- Urinalysis: day 1 of every cycle
- Serologies: if clinically indicated
- Pregnancy Testing: every 4 weeks (day 1 of each cycle). Pre-menopausal women of childbearing potential only
- Adverse events: in all study visits
- Concomitant medications: in all study visits
- Blood sample: two CPT tubes of 7 ml will be obtained before treatment administration at D1C1 and D1C2.

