### 12.2. Sample size

Patients with advanced TNBC that have received and experienced disease progression to the first/second line treatment are candidates to this trial. Patients that have received three or more treatment lines would be excluded.

Sample size has been calculated based on the primary objective of this clinical trial, to determine 3-months PFS of the palbociclib plus binimetinib in advanced TNBC, in patients with activation of ERK and/or CDK4/6.

Previous studies shown that the 3-months PFS in patients receiving chemotherapy in advanced TNBC was about 25% [44]. To accept the treatment efficacy we will assume that the 3-months PFS in patients treated with palbociclib plus binimetinib will be at least 50%. An overall sample size of 25 patients achieves 80% power at a 0.05 significance level (alpha) to accept the efficacy of palbociclib plus binimetinib in advanced TNBC. An accrual time of 12 months and follow-up time of 12 months (treatment and follow-up time) and 2 sided test have been considered in the sample size calculation.

Sample size has been calculated with one-sample survival method [45].

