### 8.2. Primary efficacy endpoint. PFS

Progression-free survival (PFS) is defined as the elapsed time, in months, between the start of treatment until the documentation of disease progression (radiological RECIST v1.1 or clinical) or death due to any cause, whichever occurs first. For subjects who are alive and not present disease progression at the time of data cut-off for analysis, PFS will be censored at the last tumor assessment date, if no one tumor assessment date is available PFS will be censored at start of treatment date.

PFS will be analyzed according to the Kaplan-Meier method. Kaplan-Meier survival curves and the median estimation will be reported, along with associated 95% CI. In order to response to primary end point, PFS rate at 3 month will be estimated and the 95% CI will be reported. In addition, PFS rate at 1 year with 95% CI will be calculated.

In addition, PFS will be evaluated by mutation ERK and CDK4/6.

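### The protocol contradicts itself on tumour scans after a stop without progression, so censoring of the primary PFS endpoint can depend on outcome, with a bias of uncertain direction

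*Protocol*

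**What the plan says.** The rules on tumour assessment stand in five places in the protocol.

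- Section 10, schedule footnote 14: "Tumor evaluation will be performed every 8 weeks until confirmed PD".
- Section 10.2: the 8-weekly scan appears in a list of procedures performed during study treatment.
- Section 10.3: one scan at the end-of-treatment (EOT) visit when the reason for stopping is not progression.
- Section 10.4: "The following procedures will be performed at Safety follow-up visit at day 30 and 6 months after last study dosage". The list that follows has no tumour evaluation, and the safety follow-up cell of the tumour-evaluation row in the schedule table is empty.
- Section 8.2: "The investigator will be requested to collect all patient data until she leave the study treatment".

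On the analysis side, protocol 12.4 and SAP 8.2 define PFS up to progression or death from any cause, with no restriction to time on treatment. SAP 8.2 accepts radiological or clinical progression. For a patient alive and without progression at data cut-off, "PFS will be censored at the last tumor assessment date"; protocol 12.4 says much the same. The SAP reports PFS at 3 months (primary) and at 1 year. It describes no sensitivity analysis for censoring.

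**The concern.** No visit list schedules a scan after the EOT scan for a patient who stops without progression. Read literally, footnote 14 would keep her on 8-weekly scans, but its markers sit in the on-treatment cells of the table, so a site can fairly read it either way. With 25 patients at 8 sites, different sites may follow different rules.

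If the visit lists are followed, the censoring depends on outcome. A patient who stops for toxicity and later dies is an event if the death is known. A patient who stops and later progresses, but is alive at cut-off, goes back to her EOT scan as censored because nobody looked. The Kaplan-Meier estimate then rests on an assumption that the plan neither states nor tests: that these patients would have fared like those still being scanned.

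Early toxicity stops are foreseeable. Protocol 8.1 names several toxicity grounds for withdrawal, and 8.3 does not replace patients lost to toxicity in the first cycle. Each such patient is 1/25 = 4% of the planned sample.

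**Working it through.** **Design figure.** Inputs from protocol 12.2: null 25%, alternative 50%, two-sided alpha 0.05, power 80%, N = 25. A normal approximation on the 3-month proportion, with no censoring before 3 months, gives

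n = (1.96 × √(0.25 × 0.75) + 0.842 × √(0.5 × 0.5))² / 0.25² = (0.849 + 0.421)² / 0.0625 = 25.8.

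Power at N = 25 is 78.9%. The planned 25 is reproduced closely enough, so the sample size is not in question. This reproduction does take 3-month status as known for every patient.

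**Which stops matter.** Three months is 3 × 30.44 / 7 = 13.0 weeks. Scans at weeks 8 and 16 fall at 1.84 and 3.68 months. The last scheduled scan before the 3-month point is therefore week 8. A patient who stops before it loses the only scheduled scan that would inform her 3-month status. Stops after week 13 cannot affect the 3-month rate, but they do affect median and 1-year PFS.

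**Bounds without a hazard assumption.** Suppose k of 25 patients stop before week 8, are progression-free at the EOT scan and are censored there before any event, and x of the other 25 − k are progression-free at 3 months. The reported rate is x/(25 − k). Continued scanning could give anything from x/25 (all k progress) to (x + k)/25 (none do). The documents give no k; 3 and 5 are illustrations. Exact (Clopper-Pearson) 95% intervals are in brackets.

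| k | Reported | All k progress | None progress |
|---|---|---|---|
| 3 | 11/22 = 50% (28-72%) | 11/25 = 44% (24-65%) | 14/25 = 56% (35-76%) |
| 5 | 10/20 = 50% (27-73%) | 10/25 = 40% (21-61%) | 15/25 = 60% (39-79%) |

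In both worst cases the lower limit falls below the 25% null, although the reported lower limit lies above it.

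**Likely direction.** A simulation compared two rules under the protocol's own schedule (scans at weeks 8 and 16, EOT scan at a non-progression stop): 8-weekly scans continue after the stop, or they end at the EOT scan. Assumptions, none of them from the documents: exponential event times with 50% on-treatment PFS at 3 months; 10-30% at risk of stopping for toxicity between weeks 0.5 and 8; off-treatment hazard 1 to 3 times on-treatment; 0-30% of events being clinical progression or death, counted when they occur. Results at 30% stopping:

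| Hazard ratio off/on treatment | Clinical PD or death | Scans continue | Scans end at EOT | Shift (points) |
|---|---|---|---|---|
| 1 | 0% | 65.3% | 60.7% | -4.6 |
| 1.5 | 0% | 63.4% | 60.6% | -2.8 |
| 2 | 0% | 61.9% | 60.6% | -1.3 |
| 1 | 30% | 60.7% | 57.5% | -3.2 |
| 1.5 | 30% | 58.5% | 56.4% | -2.1 |
| 2 | 30% | 56.7% | 55.6% | -1.1 |

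At a ratio of 3 the shift turns positive, to at most about +1.6. Over the whole range it runs from about -5 to +1.6 points. For stops between weeks 8 and 13 (20-30% stopping, ratios 1 to 2) it stays within about 1 point.

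Two forces oppose each other. The EOT scan dates some progressions earlier than week 8, while patients found progression-free there leave the risk set before that scan; this pulls the estimate down. A higher hazard after stopping means that the censored patients are the worse ones; this pulls it up.

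The range also supposes that clinical progression and death after stopping reach the database. If they do not, as a literal reading of section 8.2 allows, the shift moves upward: at a ratio of 2, with 30% stopping and 30% such events, it goes from -1.1 to +0.9.

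**The case against.** The best defence is that this is an ambiguity and not a prohibition. Section 10.4 is a safety visit and is silent on scans; it does not forbid them. Footnote 14, attached to on-treatment cells, is compatible with 10.2. Section 8.2 also requires withdrawn patients to complete the withdrawal procedures, which include the EOT scan. SAP 8.2 counts progression or death whenever it occurs and does not censor at drug stop, so the definition of the endpoint is sound. Dose reductions, interruptions and possible continuation on one drug (protocol 9.1.1.4, 9.2 and 9.3) keep many patients with toxicity on study and on scans. All of this stands, and it narrows the point. It does not supply the missing post-EOT scan or tell sites which rule to follow.

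Two stronger readings are tempting, and the documents support neither.

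- A reader might infer that the gap inflates 3-month PFS. A continuous-time calculation suggests so: with 50% on treatment, a 20% risk of stopping and a doubled hazard afterwards, true PFS is 47.1% against a censored estimate of 50.0%. But it assumes that progression is seen the moment it happens, gives the EOT scan no role, and loses every event after the stop. Under the actual schedule the same doubled hazard gives a small negative shift when later clinical progression and deaths are counted.
- A reader might take the 61% dose-reduction figure in protocol 5.2 as evidence of frequent early stops. It concerns dose reduction in melanoma, not stopping. The documents give no rate of stopping for toxicity.

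**Conclusion.** The point holds as a contradiction in the protocol that bears on the primary endpoint. Following the visit lists gives outcome-dependent censoring and lost information, and sites may apply different rules. It does not establish an optimistic bias. The sign depends on the off-treatment hazard and on whether later clinical progression and deaths are collected. The shift of about -5 to +1.6 points rests on assumed stopping rates and hazards and on later known events being counted.

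The bounds need no hazard assumption. Three early-censored patients leave a reported 50% anywhere between 44% and 56%; five leave it between 40% and 60%. These are extremes and not expected values, and the number of such patients is unknown. If few patients stop before week 8, the 3-month rate is hardly touched and the issue is mainly one for median and 1-year PFS.

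**What to change.** - **Protocol 8.2, 10.3, 10.4 and the schedule table:** reconcile with footnote 14. State that, for patients who stop without progression, tumour assessment and PFS data collection continue on the 8-weekly schedule until progression, death, withdrawal of consent or data cut-off.
- **Protocol 8.1 and 8.2:** separate stopping treatment from leaving the study, so that a toxicity stop does not by itself end data collection.
- **SAP 8.2:** add a sensitivity analysis for patients censored before 3 months, either best/worst-case bounds as above or early stops counted as failures. Report how many patients are affected and why. The event definition needs no change.

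The cost is a protocol clarification, a few scans that footnote 14 already implies for patients who stop early, and a small addition to the analysis. The sample size stays as it is.

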## **11. ASSESSMENT OF SAFETY / ADVERSE EVENTS**

Safety information should be collected in clinical studies in an efficient and consistent way. Adverse events must be identified and notified rapidly to identify possible risks to patients and satisfy regulatory requirements for notification of adverse events.

### **11.1. Definitions**

#### **11.1.1. Adverse event (AE)**

An AE is any undesired experience that occurs in a patient participating in clinical research that is associated in time with the use of a medicinal product, whether or not it is considered to be related to the investigational products. Therefore, an adverse event can be any unintentional unfavorable sign (including an anomalous laboratory result), symptom or disease that is associated in time with the use of a medicinal product, whether or not it is considered to be related to the product. Pre-existing diseases that worsen during the study shall be notified as Adverse Events.

AEs include pre- or post-treatment events that occur as a result of study procedures (e.g. invasive procedures or modification of the patient's previous medication).

#### **11.1.2. Serious adverse event (SAE)**

A SAE is an undesired medical experience that, at any dose:

- Results in death.
- Is life-threatening: (NOTE: The term "life-threatening" refers to the fact that, according to investigator criteria, the patient is at risk of death as a result of this event. Nevertheless, this definition does not consider the situation in if the AE had been more severe, patients had been in an immediate risk of death).
- Results in the patient's hospitalization or prolongs a previous hospitalization (NOTE: In general, hospitalization means that the patient has remained [at least 24 hours] in the hospital or emergency room. Complications that occur during a hospitalization are AEs. If a complication prolongs hospitalization or satisfies any of the other criteria for seriousness, then the event will be considered SAE. When any doubt exists as to whether a "hospitalization" has taken place or was necessary, the AE will be considered serious. The hospitalization to implement scheduled treatment of a disease present before the subject entered the study and that has not worsened with respect to baseline is not considered an AE) Hospitalizations for social reason are not consider an AE.
- It produces disability or incapacity (NOTE: Disability refers to an important alteration in a person's capacity to carry out his or her own daily living tasks, not minor clinical ailments such as headaches, nausea, vomiting, diarrhea, flu or accidental injuries (such as a sprained ankle), that can interfere with the functions of daily life, but do not alter them in an important way).
- It originates a congenital anomaly or birth defect.
- It is medically important, meaning medically important adverse event that the investigator regards as serious that did not strictly meet the criteria above but may have jeopardized the patient or required intervention to prevent one of the outcomes listed above.

### **11.1.3. Additional considerations**

Alterations in laboratory parameters (hematology, biochemistry or urine analysis), as well as anomalous results of other studies (such as ECGs, radiology, measurements of vital constants), including those that deteriorate in relation to baseline, should be recorded as AEs or SAEs if, in the medical and scientific opinion of the investigator, they are clinically relevant.

On the contrary, clinically significant alterations in safety parameters that are associated with the study disease are not characterized as AEs or SAEs unless the investigator thinks that they are more serious than would be expected considering the state of the patient.

Lack of efficacy (i.e., disease progression) is a disease-related event and should not be classified as a SAE. Death as a result of disease progression is also excluded from the definition of SAEs.

### **11.1.4. Adverse reaction**

Any harmful and non-intended response to a drug including adverse reactions derivative from any use apart from terms of commercialization authorization, abuse, and medication error. It exists a confirmed causality relationship with the administered medication.

## **11.2. Characteristics of an adverse event**

### **11.2.1. Seriousness**

See Serious Adverse Event definition (11.1.2 Serious Adverse Event (SAE)).

### **11.2.2. Causality assessment**

The investigator has the obligation to establish the relation of causality between the investigational product administration and the adverse event (serious or not). "A reasonable possibility" is proposed to define cases in which there are facts/proof or arguments suggesting a causal relation, more than a relation that cannot be excluded. The investigator will use his or her clinical judgment to determine the relation. Alternative causes, such as the natural history of underlying diseases, concomitant treatment, other risk factors and the temporal relation between the event and the investigational drug will be considered and investigated. The investigator will also consult the investigator's brochure/summary of product characteristics in making the evaluation.

There may be situations in which a SAE occurs and the investigator has only minimal information to include in the initial report to the Sponsor. Nevertheless, it is very important that the investigator evaluate the causality of each event before the initial transmission of data to the Sponsor. The investigator can change his or her opinion about causality based on the information that appears during follow-up, which is why the SAE report may have to be modified. The evaluation of causality is one of the criteria that determine whether a case is compliant or not with the criteria of notification of the Health Authorities.

### **11.2.3. Expectedness**

An unexpected adverse reaction is any untoward and unintended response that is related to study drug at any dose that is not described in the applicable product information (eg, investigators brochure for an unauthorized investigational medicinal product or summary of product characteristics for an authorized product).

APICES/Sponsor will classify a Serious Adverse Reaction as expected or unexpected according to the Reference Safety Information collected in investigator brochure or summary of product characteristics of investigational product, as appropriate.

